4.2 Rationale

Due to cost, time constraints, and limited patient population (there are approximately 80 kidney transplant recipients at UNC-CH), we are not able to conduct the ideal randomized, double-blind, two-group parallel study. Rather, we are proposing a study design that is practical, given the available resources and still investigates the safety and effectiveness of using genotype-guided tacrolimus dosing.

In this study, a comparison of the primary and secondary endpoints will be conducted between kidney transplant recipients who underwent prospective pharmacogenomic-guided tacrolimus dosing strategy (pharmacogenomic group) and patients who received standard tacrolimus dosing regimen historically and prospectively (control group). Although genotyping the control group can be more expensive and time consuming, knowing the genotype information of the control group will allow us to do the following: 1) identify if the control and pharmacogenomic groups are comparable with regards to genotype; and 2) conduct a subgroup analysis based on treatment and genotype, comparing the outcomes and tacrolimus levels of patients who are *CYP3A5*1/*1*, *CYP3A5*1/*3*, or *CYP3A5*3/*3* who received standard therapy versus genotype-guided dosing.

4.3 Patient Selection

The study schemas for the pharmacogenomic and control groups are displayed in Figure 2.

Figure 2: Study Schema

[figure not shown]

Figure 2. The overall study schematic for the pharmacogenomics group is shown on the left, and the study schematic for the control group is shown on the right.

Briefly, patients currently on the waitlist to receive kidney transplantation at UNC-CH who are being seen by the multi-disciplinary kidney transplantation team will be screened for eligibility. At the pre-intervention assessment (Study Day 0), buccal swab samples for genotyping will be collected on all eligible patients who provided informed consent (performed in real time). All buccal swab samples collected will then be

de-identified and sent to Cancer Genetics Incorporated (CGI) for *CYP3A5* genotyping. Results of the genotyping test will be incorporated into electronic medical record (EMR) in addition to the genotype-guided dosing recommendation for each patient. The initial tacrolimus dose will be based on the pharmacogenomic-guided treatment algorithm described in [Section 6.2.1](#).. Eligible patients who consented to receive genotype-guided tacrolimus dose will enter the pharmacogenomic group and will receive the initial tacrolimus dosing based on genotype results following kidney transplantation (Study Day 1). Subsequent tacrolimus dosing will then be adjusted according to trough concentrations (C₀) and therapeutic target concentrations of 8-10 ng/mL (0 to 4 months), 6-8 ng/mL (5 to 12 months), and 5-7 ng/mL (>12 months). Dose adjustments and therapeutic drug monitoring will be conducted according to standard UNC-CH procedure. Hence, the genotype-guided dosing recommendation for tacrolimus only refers to the initial tacrolimus dose. All patients in the pharmacogenomic group will be followed from Study Day 2 and up to 12 months from the initiation of the first tacrolimus dose to assess long-term outcome (Follow-up Period). Safety and efficacy measures will be evaluated throughout the study per UNC-CH kidney transplant procedure.

As the arrival of the donor kidney may come quickly and unexpectedly, it is possible that enrolled subjects may receive kidney transplantation prior to the incorporation of the *CYP3A5* genotype result into EMR. In this case, patients will receive tacrolimus based on current standard tacrolimus dosing (0.1 mg/kg/day given in two divided doses) and will be included in the control group (prospective controls). Throughout the study, safety and efficacy measures will be evaluated in the prospective controls per UNC-CH kidney transplant procedure. These patients will also be followed from Study Day 2 and up to 12 months from the initiation of the first tacrolimus dose to assess long-term outcome (Follow-up Period).

Additionally, age-, race-, and disease-matched patients who had previously received kidney transplantation with standard tacrolimus dosing will also be asked to give consent for genotyping (historical controls). These patients will also be included in the control group and their safety and efficacy data will be collected retrospectively for up to 12 months from the initiation of first tacrolimus dose. Hence, the control group will consist of both historical controls and potentially few prospective controls, if the scenario described above occurred.

4.4 Genotyping and Dosing Administration

The *CYP3A5* 6986A>G (rs776746) variant is ideal for a pharmacogenomic study as it has a high estimated allele frequency across various populations, including Whites (82% to 95%), Japanese (85%), Southeast Asians excluding Japanese and Chinese (67%), Chinese (65%), Pacific Islanders (65%), Southwest American Indians (40%), and African Americans (33%) (Lamba, 2012). At the UNC-CH multidisciplinary kidney transplantation team, we see approximately 80 patients for kidney transplantation per year. Of those 80 patients, approximately 60% are Whites and 40% are African Americans. We therefore expect that the *CYP3A5* 6986A>G (rs776746) variant will be relatively frequent in our study population. In addition, to be able to effectively compare outcomes between expressers and nonexpressers as well as between genotyped and nongenotyped subjects, we will make every effort to enroll African Americans to the study so as to get equal numbers of Caucasians and African Americans in our study.

At study enrollment, buccal swab samples will be obtained for genotyping of the *CYP3A5* 6986A>G (rs776746) variant. Based on the genotyping result, patients will be categorized into two categories:

- *CYP3A5* expressers (*CYP3A5**1/*3 and *CYP3A5**1/*1)
- *CYP3A5* nonexpressers (*CYP3A5**3/*3)

Patients will then receive the initial tacrolimus dose based on the genotype-guided dosing algorithm outlined in [Section 6.2.1](#). Subsequent tacrolimus dosing will then be adjusted according to trough concentrations and therapeutic target concentrations.

5 Subject Selection and Withdrawal

5.1 Inclusion Criteria

All new kidney transplant recipients aged 18 to 65 years who are admitted at UNC-CH and provided informed consent will be included in this study.

5.2 Exclusion Criteria

Patients will be excluded from participating in the study to receive genotype-guided tacrolimus dosing if he/she meets any of the exclusion criteria described below.

- Recipients who did not consent to participate in the study.
- Highly sensitized patients (ie, pretransplant T or B cell flow crossmatch positive)
- Recipients of ABO incompatible kidney transplant
- Recipients with preformed donor-specific antibodies (DSA)
- HLA identical kidney transplant
- Recipients of non-kidney transplant
- Recipients of repeat transplant if they are on immunosuppression at the time of transplant
- Patients using medications that have known pharmacokinetic (PK) drug interaction with tacrolimus
- Patients in whom tacrolimus therapy is contraindicated

5.3 Patient Recruitment and Screening

Patients receiving pretransplant care for kidney transplantation at UNC-CH will be screened for eligibility based on the inclusion/exclusion criteria described in [Sections 5.1](#) and [5.2](#). Following acquisition of consent, buccal swab samples will be collected for genotyping. Eligible patients who consented will receive genotype-guided dose for the initial tacrolimus dosing following kidney transplantation.

Subsequent tacrolimus dosing will then be adjusted according to trough concentrations and therapeutic target concentrations.

For the historical controls, age- and disease-matched patients who had previously received kidney transplantation with standard tacrolimus dosing will also be asked to give consent for genotyping (historical controls) during one of their post-transplant visit. Eligible patients who consented will be included in the control group and their safety and efficacy data will be collected retrospectively for up to 12 months from the initiation of first tacrolimus dose.

In addition, to be able to effectively compare outcomes between expressers and nonexpressers as well as between pharmacogenomic and control groups, we will make every effort to enroll African Americans to the study, including showing genuine interest to subjects' well-being during one-on-one interactions, referring to them by their last names until given permission to use their first names, and using noninvasive means to collect samples (Johnson et al. 2011; Spence and Oltmanns 2011), so as to get equal numbers of Caucasians and African Americans in our study.

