4.1 General Design

This is a single-center study of pharmacogenomic-guided tacrolimus dosing and drug monitoring in kidney transplant recipients (Figure 1). The pharmacogenomic group will partake in a 12-month study comprising of two periods, Genotype-Guided Initial Dosing Intervention and Follow-up.

Following screening, acquisition of consent, and genotyping, a comprehensive medical chart review will be conducted for the control group. Twelve-month post-transplant data will be collected in the control group with timepoints that match with the pharmacogenomics group.

Figure 1: Study Design

[figure not shown]

Figure 1. This figure provides the general study design for the study, which comprises of the Screening and two study periods (Intervention and Follow-up) for the pharmacogenomic group. After consent and genotyping have been conducted, a comprehensive medical chart review will be conducted for the control group.

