7.1 Pre-intervention Assessments

The following procedures will be performed at Study Day 0, prior to initiation of the genotype-guided initial tacrolimus dose

- Screening for eligibility
- Acquisition of informed consent
- Buccal swab sample collection
- Hematology, clinical chemistry, urinalysis, eGFR, medical history, and physical exam

- Genotyping

7.2 *Pharmacogenomic Intervention*

On Study Day 1, Eligible patients who consented will receive genotype-guided dosing only for the initial tacrolimus dosing (0.1 mg/kg/day for CYP3A5*3/*3 or 0.2 mg/kg/day for CYP3A5*1/*1 or CYP3A5*1/*3). In addition, the following safety and efficacy parameters will be collected: hematology, clinical chemistry, urinalysis, adverse event (AE) and renal function assessments, medical history, physical exam, tacrolimus levels, and immunosuppressive and tacrolimus therapy modifications.

7.3 *Post-intervention or Follow-up Assessments*

Following administration of the initial genotype-guided tacrolimus dose, protocol-driven therapy will cease, and standard of care for tacrolimus dose adjustment and monitoring will be initiated. Efficacy and safety data, including AE assessments, renal function, and tacrolimus levels, will still be collected at each subsequent standard follow-up interval post Study Day 1 and up to 12 months of the initial tacrolimus dose.

Table 1: Schedule of Events

Procedure	Study Day 0	Study Day 1	3-day Follow-up	7-day Follow-up	Week 2 Follow-up	Week 3 Follow-up	Week 4 Follow-up	3-month Follow-up	6-month Follow-up	9-month Follow-up	12-month Follow-up
Screening	x										
Informed consent	x										
Buccal swab sample	x										
Medical history	x										
Drug therapy assessment	x	x	x	x	x	x	x	x	x	x	x
Physical Exam	x	x	x	x	x	x	x	x	x	x	x
Clinical chemistry	x	x	x	x	x	x	x	x	x	x	x
CBCs with differentials	x	x	x	x	x	x	x	x	x	x	x
Urinalysis	x	x	x	x	x	x	x	x	x	x	x
CrCl	x	x	x	x	x	x	x	x	x	x	x
eGFR	x	x	x	x	x	x	x	x	x	x	x
Genotyping	x										
Initiation of genotype-guided dose		x									
Tacrolimus level		x	x	x	x	x	x	x	x	x	x
AE assessments ¹		x	x	x	x	x	x	x	x	x	x
Efficacy assessments ²		x	x	x	x	x	x	x	x	x	x

Abbreviations: AE=adverse event; BPAR = biopsy proven acute rejection; CBC = complete blood count; CrCl = creatinine clearance; eGFR = estimated Glomerular Filtration Rate.

¹The AE assessment will be conducted using the AE form (see AE Attachment). AEs may be assessed during an in-person clinic visit or a scheduled phone call.

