8.4 Matching Strategy

As there are confounding variables, including age, race and disease state that may impact the results of the study, our study design incorporates an overall matching strategy, so that we can identify a well-matched control group. First, to control for differences in care over time, patients in the pharmacogenomic group will be matched to controls enrolled from 2010 to present. This time period was selected as there had been no major changes in standard of care or treatment regimen since 2010. After eligibility is met, control patients will be selected to match the pharmacogenomic group using a computerized matching algorithm that has been optimized to match baseline demographic and disease characteristics that have been identified a priori as likely to influence the treatment response to tacrolimus. To balance the trade-off between minimizing bias and maximizing matched sample size, a systematic approach will be conducted to identify the number of matched control patients for each patient in the pharmacogenomic group. This approach will include the following steps: 1) run the desired matching algorithm, starting with 1:1 (one control to one patient in the pharmacogenomic group) matching and iterating until the maximum desired number of potential controls per treated subject is reached; 2) for each iteration, test for covariate balance; and 3) generate numeric summaries and graphical plots of the balance statistics across all iterations in order to determine the optimal number (Linden and Samuels 2013).

The selection of patients for the control group using a matching algorithm will be conducted by an independent statistician in a blinded and unbiased manner. The statistician will have no knowledge of survival outcome, other outcome data, and genotype.

9 Safety and Adverse Events

Safety will be assessed throughout the study by evaluating physical exam, clinical chemistry, urinalysis, hematology, renal function, and incidence of adverse events (ie, graft rejection, graft loss, renal impairment, drug-related adverse events, tacrolimus toxicities, and death).

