9.2 Recording of Adverse Events

AEs will be collected following kidney transplantation. AEs are recorded as part of routine standard of care for kidney transplant recipients.

At each contact with the subject, the investigator must seek information on AEs by specific questioning and, as appropriate, by examination. Information on all AEs should be recorded immediately in the source document. All clearly related signs, symptoms, and abnormal diagnostic procedures results should be recorded.

All AEs occurring during the study period must be recorded. The clinical course of each event should be followed until resolution, stabilization, or until it has been determined that the study treatment or participation is not the cause. SAEs that are still ongoing at the end of the study period must be followed up to determine

the final outcome. Any SAE that occurs after the study period and is considered to be possibly related to the study treatment or study participation should be recorded and reported immediately.

All AEs, both serious and nonserious, and deaths that occur during the patient's study participation will be recorded. All SAEs should be monitored until they are resolved or are clearly determined to be due to a patient's stable or chronic condition or intercurrent illness(es).

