10.4.2 Historical Data

Historical data from the control group will be obtained from 2010 until the end of study period. The historical controls will consist of age- and disease-matched patients who met eligibility criteria and have had previously

received kidney transplantation with standard tacrolimus dosing. These patients will also be asked to give consent for genotyping during a standard routine follow-up visit post-transplantation. Eligible patients who consented will be included in the control group and their safety and efficacy data will be collected retrospectively for up to 12 months from the initiation of the first tacrolimus dose.

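### Historical controls must survive to a post-transplant consent visit to be counted, so early control deaths drop out and the death comparison is biased against genotype-guided dosing.

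*Combined protocol and SAP*

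**What the plan says.** Section 5.3 states that past recipients "will also be asked to give consent for genotyping (historical controls) during one of their post-transplant visit". Section 10.4.2 repeats the rule: "These patients will also be asked to give consent for genotyping during a standard routine follow-up visit post-transplantation". Consent is a condition of entry: "Eligible patients who consented will be included in the control group and their safety and efficacy data will be collected retrospectively". The look-back starts at the first tacrolimus dose and covers at most 12 months. Section 4.1 puts the chart work last: "Following screening, acquisition of consent, and genotyping, a comprehensive medical chart review will be conducted for the control group".

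The pharmacogenomic group enters differently. Under Section 4.3, at Study Day 0, "buccal swab samples for genotyping will be collected on all eligible patients who provided informed consent". Section 7.1 places consent in the same window: "The following procedures will be performed at Study Day 0, prior to initiation of the genotype-guided initial tacrolimus dose". For deaths, Section 9.2 says: "All AEs, both serious and nonserious, and deaths that occur during the patient's study participation will be recorded".

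Death is one component of the adverse-outcome endpoint in Section 3.2. Sections 3 and 4.2 plan a between-group comparison of the secondary endpoints. Section 8.3 estimates the incidence of these outcomes by Kaplan-Meier and mentions no delayed entry.

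**The concern.** The two groups have different entry rules for the same clock. Time runs from the first tacrolimus dose in both, but a historical control must also be alive at a later clinic visit. The interval between first dose and consent is immortal time for that control. Deaths in it are removed from the control group, while deaths in the same interval count in the pharmacogenomic group.

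For this mechanism the direction is fixed. With no true difference, survival looks worse under genotype-guided dosing, and a real survival benefit would be understated. Clinical outcomes and safety are stated aims of the study. A reader of the report could not detect the problem, because the plan does not call for reporting time from transplant to consent or the number of past recipients who had already died.

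**Working it through.** **1. Does any provision restore the lost deaths?**
- Section 8.4: "After eligibility is met, control patients will be selected to match the pharmacogenomic group using a computerized matching algorithm". The matching statistician is blind to survival, but blinding cannot bring back people who never enter. It is unclear whether matching precedes consent (as 5.3 and 10.4.2 read) or follows it. The deaths are lost in either order.
- Section 8.3: the ITT principle covers only those included.
- Section 10.4.3: the missing-data text concerns tacrolimus levels.
- Section 1.1 under Ethical Considerations: a surrogate may sign, but recruitment takes place at the patient's own visit and needs a buccal swab.
- Section 4.3: prospective controls escape the selection, but are expected to be few.

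**2. The plan's own figure.** Section 8.2 uses 40% against 60%, two-sided alpha 0.05 and 90% power. With mean proportion 0.5, n = [1.960·√(2·0.5·0.5) + 1.2816·√(0.24 + 0.24)]² / 0.20² = (1.386 + 0.888)² / 0.04 = 129.3, so 130 per group and 260 in total. The sample size reproduces and is not affected by this point.

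**3. Falsely significant harm on death alone.** Inputs: 130 per group (8.2), two-sided 0.05 (8.3). Assumptions: equal true 12-month mortality p in both groups, and a share s of control deaths that the entry rule leaves visible. Two-sided Fisher p-values for deaths in the pharmacogenomic and control groups: 5 vs 0, 0.060; 6 vs 0, 0.029; 7 vs 1, 0.066; 8 vs 1, 0.036. False harm is the probability of p<0.05 with more pharmacogenomic deaths, by exact enumeration. Pharmacogenomic deaths are Bin(130, p). Control deaths are Bin(130, s·p), except that for s = 1/2 they are Bin(65, p) counted over 130.

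| Share of control deaths visible | p = 1% | 2% | 3% | 5% |
|---|---|---|---|---|
| All (no selection) | 0.1% | 0.4% | 0.8% | 1.1% |
| 1/2 | 0.1% | 1.5% | 4% | 10% |
| 31% | 0.1% | 2.3% | 8% | 21% |
| 1/12 | 0.2% | 4% | 15% | 48% |
| None | 0.2% | 5% | 20% | 64% |

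With none visible, expected deaths are 1.3, 2.6, 3.9 and 6.5 against 0, so the spurious difference equals p. The uncorrected chi-square gives larger values for that row (4%, 26%, 55%, 89%), so Fisher is the cautious choice.

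**4. Where the plan may fall.** Section 4.4 gives about 80 transplants a year. From 2010 to 2016 (the latest year in the reference list, used as an assumed approach date) that is 6 × 80 = 480, of whom 400 (83%) are past month 12.
- Controls spread evenly over those years, constant hazard (both assumed): 80/480 × 1/2 = 1/12 of control deaths visible.
- All 80 recipients of the last year become controls: 130 − 80 = 50 are still past month 12, and 80 × 1/2 / 130 = 31% visible.
- Controls transplanted during the study and approached early would raise these shares.

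**5. Within the adverse-outcome composite.** With independent other events in a fraction q, mortality m and every control death lost, the risks are 1 − (1 − q)(1 − m) and q, so the shift is (1 − q)·m. The test is the uncorrected chi-square. Values run over m = 1%, 2%, 3% and 5%.

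| q (assumed) | Shift, points | False harm | No selection |
|---|---|---|---|
| 20% | 0.8, 1.6, 2.4, 4.0 | 3.6%, 5.0%, 6.8%, 11.8% | 2.5% |
| 50% | 0.5, 1.0, 1.5, 2.5 | 3.3%, 3.9%, 4.6%, 6.4% | 2.7% |
| 80% | 0.2, 0.4, 0.6, 1.0 | 2.7%, 3.0%, 3.3%, 3.9% | 2.5% |
| 90% | 0.1, 0.2, 0.3, 0.5 | 2.7%, 2.9%, 3.0%, 3.4% | 2.5% |

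**The case against.** The case against accepts the mechanism and disputes its weight.

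- **No stated test of death alone.** Death is one item in one of five secondary endpoints, and Section 8.3 promises Kaplan-Meier estimates. This stands in part. A comparison of secondary endpoints is planned and Section 8.3 offers chi-square or Fisher for categorical data, so a test is possible but not stated. The Kaplan-Meier estimate is biased whether or not it is tested.
- **The composite may hardly move.** Section 3.2 counts an eGFR of 60 to 89 as mild renal impairment and includes adverse drug events, so nearly every recipient could qualify. This stands: at 90% other events the shift is at most 0.5 points for mortality up to 5%. Death read separately is the part at risk.
- **The size is assumed.** At 1% mortality false harm stays at or below 0.2%. The large values need 3% to 5% mortality and mostly late consent. This stands, and it is why ranges are given.
- **Some pharmacogenomic deaths may also be missed.** Section 5.4 allows voluntary withdrawal and Section 8.2 expects under 5% dropout. This is true but small, and it is not tied to survival as the control rule is.
- **Other biases, such as change in care over time, may offset this one.** This stands for the net result. It does not change the direction of this mechanism.

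**Conclusion.** The concern holds. Followed as written, the plan leaves out control deaths that occur before the consent visit and keeps the corresponding pharmacogenomic deaths, so this part of the death comparison runs against genotype-guided dosing. Confidence in the mechanism and its direction is high. The size is not fixed by the documents. At an assumed 2% to 5% mortality, with 1/12 to 1/2 of control deaths visible, false harm on death alone ranges from 1.5% to 48%, against 0.4% to 1.1% without selection.

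The limits are as follows. Graft loss may be affected too, but its direction cannot be established from the documents. Nothing is claimed for rejection, renal impairment or other adverse events. The Day 3 and Day 7 primary endpoint is not directly affected. Controls approached soon after transplant lose few or no deaths. This should be fixed, but it does not undermine the primary analysis.

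**What to change.** 1. In Sections 5.3, 8.4 and 10.4.2, identify and match controls from all eligible transplants since 2010, regardless of later survival or clinic attendance. Ask the IRB for a waiver of consent for non-genetic chart outcomes, and require consent only for genotyping. Use this full set for death and graft loss. Restrict the genotype balance check and genotype subgroups of Section 4.2 to consenting controls. State in Section 8.3 which set serves the primary endpoint; it can remain the consenting matched controls.
2. In any case, report how many eligible past recipients had died, had lost the graft, were not reached or declined, together with the time from transplant to consent.
3. If no waiver is granted, report death, and any composite containing it, descriptively and do not test it against historical controls. Delayed entry at the consent date helps only for controls who consent within month 12; later consenters contribute no 12-month risk time.

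**Cost.** The full version needs one IRB request, revised wording and more chart abstraction. To keep 130 consenting controls at assumed consent rates of 90%, 70% or 50% takes 130/0.9 = 145, 130/0.7 = 186 or 130/0.5 = 260 matched charts, from roughly 480 before exclusions. Some controls will lack genotype, and two control sets must be kept apart in the report. Items 2 and 3 alone need only wording and simple counts.
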